1 INTRODUCTION

Contact lens (CL) dropout is a problem for established CL wearers but also in new wearers (neophytes). A recent retrospective study on neophytes showed that 1 in 4 patients discontinued lens wear within the first 12 months with the primary reasons being vision (41%), comfort (36%) and lens handling problems (25%).

Alcon has recently launched a new daily disposable contact lens (Precision1) and in this study the initial subjective handling experience of neophyte CL wearers will be determined. The handling experience with this new lens will be compared to a daily disposable lens which has been on the market for numerous years already (1-Day ACUVUE Moist).

2 OBJECTIVES

The objectives of the study are:

- Subjective ratings of lens handling for insertion and removal as determined during the handling training component of Visit 1 (Or Visit 1B-R) (i.e. the first exposure of the participants to handling contact lenses; 0 to 100 scale) for each lens.
- Additional "general" handling questions to be evaluated may include "Ease of opening package", "Ease of removing lens from package", "Ease of telling whether lens is inside/out" or "Stability on finger". These questions will be evaluated after training session (Visit 1 and Visit 1B-R)) and after 1 week of wear (Visit 2), using 0 100 ratings.

Primary Endpoint:

 Subjective ratings of lens handling for insertion and removal as determined during the handling training component during Visit 1 (and Visit 1B-R) (i.e. the first exposure of the participants to handling contact lenses; 0 to 100 scale)

Other Endpoints:

- Subjective ratings of comfort and handling after 1 week of wear, considering a "typical day" (0 to 100 scale)
- Lens preference after 1 week of wear for Handling for Insertion & Handling for Removal (Likert scale; including strongly prefer Lens1, slightly prefer Lens1, no preference, slightly prefer Lens2, strongly prefer Lens2)
- Subjective ratings (0 100 scale) of "general" handling questions, to be evaluated at Visit
 1 and Visit 1B-R (based on initial training) & at Visit 2 (after 1 week of wear), including

"Ease of opening package", "Ease of removing lens from package", "Ease of telling whether lens is inside/out" and "Stability on finger".

3 RATIONALE

Although CL handling is an important factor to the success of CL use in neophytes, the handling experience of Precision 1 compared to a hydrogel daily CL is unknown.

4 HYPOTHESIS

Neophyte participants will have a superior handling experience for insertion, removal, overall handling and handling preference with Precision1 DD CLs when compared to 1-Day ACUVUE Moist DD CLs.

5 MATERIALS AND METHODS

5.1 STUDY DESIGN

5.1.1 OVERALL DESIGN

This is a prospective, double-masked, contralateral wear, dispensing, single-site study with 2 study visits over the course of 1 week. Eligible participants will wear the two study lens types (L1 & L2) contralaterally for approximately 1 week (6-10 days) at least 5 days and at least 6 hours/day.

5.1.2 RANDOMIZATION

A randomization schedule will be generated using a web-based program: (for example www.randomization.com) by CORE's Data management team, and provided to the research assistants for the study. The schedule will determine which lens type (L1 or L2) will be worn on which eye for each participant. In addition, start eye for insertion/removal training will also be randomized to prevent any potential bias due to handedness/dexterity. Study investigators and participants will remain masked to the lens randomization schedule until the study is completed and the database has been locked.

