5.4.2 STUDY VISITS

Table 2 shows the summary of the 2 study visits. The total time commitment for each participant is 2hr 45 min. Participants who did not complete the handling training successfully at Visit 1, will return for Visit 1B-R (1hr) visit for additional handling training.

Visit code	Visits
1	Part A: Screening, Lens fitting (1hr) Part B: Handling training, Questionnaires, Lens dispensing (1hr)
1B-R	OPTIONAL: Handling Training (both CL types) & Dispense (only if px did not pass handling training at Visit 1) (1hr)
2	Follow-up and Exit (45 min)

Table 2: Summary of visits

Visit 1 -Part A - Screening and lens fitting (1hr)

The participant will attend the study visit wearing spectacles. The participant's eligibility for the study will be determined, including the following:

- Informed consent procedure
- Participant demographics (age, sex)
- Participant medical history/medications
- With habitual spectacles, logMAR high illumination high contrast visual acuity (HIHC VA) for OD, OS & OU
- Biomicroscopy examination (Efron scale)
 - External adnexa anomalies
 - Cornea & anterior eye assessment for scars, infiltrates
 - Bulbar & limbal redness
 - Corneal & conjunctival staining with fluorescein dye
 - Palpebral conjunctival hyperemia & roughness
- Auto refraction/auto keratometry: horizontal and vertical K readings;
- Subjective refraction/ best sphere refraction;
- Randomization: Lens type:
 - Precision 1 and 1-Day Acuvue Moist lenses will be randomized to one eye each;
- Study lens fitting –Lens types will be fit according to the randomization table the investigator will insert and remove the lenses
 - o logMAR high illumination high contrast visual acuity (HIHC VA) for OD, OS & OU;

- Power optimization if applicable;
- Lens fit assessment (Overall Lens Fit acceptance (0-4, 0.5 steps), Lens Wettability (0-4, 0.25 steps), Lens Tightness (0-100, 1 step), Lens Centration (0-3, 1 step)

С

• Confirmation of eligibility to continue to Visit 1 Part B.

Visit 1 – Part B – Handling training, questionnaires and lens dispensing (1hr)

- Randomization: Eye for contralateral handling:
 - Start eye for insertion/removal training will be randomized to prevent any potential bias due to handedness/dexterity
 - o Participant opens the lens blister packs and practices insertion & removal;
 - Insertion & removal with each lens needs to be successful 3x to be allowed to leave site with CLs

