- Confirmation of eligibility capable of insertion/removal of CLs; participants who are NOT able to remove/insert the study lenses 3x will be offered to attend a re-training session (Visit 1B-R), at which the training will be repeated. Only those participants able to insert/remove lenses at Visit 1 (or Visit 1B-R) will continue in the study.
- **PRIMARY OUTCOME VARIABLE** (only if participants have passed the CL handling training): subjective post-handling training ratings (0-100 scale, where 100 means better handling) for **each eye individually**. Separate ratings and comments for:
 - Ease of insertion
 - Ease of removal
 - General handling questions (not primary outcome variable)
- LogMAR HIHC VA for OD, OS and OU (If returning for Re-training: habitual spectacles, if lenses are dispensed today: study CL)
- Lens wear instructions (only after a successful training)
- Booking of Follow-up visit(only after a successful training)
- Lens dispense (equal number of pairs as there are days until next visit day, plus 3 spare
 pairs in case of handling issues); each px will keep the same lens type (L1 or L2) for
 each eye as randomized to for handling training (e.g. if Precision1 was used on OD for
 training, Precision1 will be worn on OD for 1 week of wear) (only after a successful
 training)

Visit 1B-R: Handling Re-Training (optional) (1hr)

Those participants who did not pass the handling training at Visit 1 will repeat this
training, following the same randomization schedule as determined during Visit 1. If a
participant passes the handling training (i.e. they successfully inserted and removed
each lens 3x), the remaining steps from Visit 1, starting at "PRIMARY OUTCOME
VARIABLE", will be completed.

- **PRIMARY OUTCOME VARIABLE** (only if participants have passed the CL handling training): subjective post-handling training ratings (0-100 scale, where 100 means better handling) for **each eye individually**. Separate ratings and comments for:
 - Ease of insertion
 - Ease of removal
 - General handling questions (not primary outcome variable)
- LogMAR HIHC VA for OD, OS and OU (If returning for Re-training: habitual spectacles, if lenses are dispensed today: study CL)
- Lens wear instructions (only after a successful training)
- Booking of Follow-up visit(only after a successful training)

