11 STATISTICAL ANALYSIS AND DATA MANAGEMENT

11.1 STATISTICAL ANALYSIS

All data will be analyzed by CORE at the University of Waterloo. Descriptive statistics will be provided on information regarding baseline variables (e.g. age, gender). Differences between lenses and differences over time will be compared using either Paired t-tests or Wilcoxon matched pairs, or using ANOVA, as applicable; statistical significance will be set at 5%. The appropriate tests will be selected based on tests of normality - non-parametric tests will be used for data not showing a normal distribution. For assessments conducted for each eye separately, the right eye will be used for analysis.

Subjective ratings for lens handling with Precision1 and 1-Day ACUVUE Moist as determined at study Visit 1 (or Visit 1B-R) (after successfully completing the lens handling training) will also be compared using superiority testing, with a margin of 5 points on a 100-point scale.

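### Optional refinement: lens-to-eye and start eye together fix which lens is handled first, but the plan does not state that they are jointly balanced and names no order term

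*Combined protocol and SAP*

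**What the plan says.** Section 5.1.2 describes a schedule that assigns the two lens types to eyes and states that "start eye for insertion/removal training will also be randomized to prevent any potential bias due to handedness/dexterity". Section 5.4.2 lists two randomisation steps at Visit 1. In Part A, "Precision 1 and 1-Day Acuvue Moist lenses will be randomized to one eye each". In Part B, "Start eye for insertion/removal training will be randomized to prevent any potential bias due to handedness/dexterity". Participants have never handled contact lenses, and each lens is inserted and removed three times on its own eye (section 5.2.3). At re-training they continue "following the same randomization schedule as determined during Visit 1". The primary ratings, for ease of insertion and ease of removal, are given only once training has been passed (section 5.4.2).

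Under section 11.1, differences between lenses are "compared using either Paired t-tests or Wilcoxon matched pairs, or using ANOVA, as applicable", and "non-parametric tests will be used for data not showing a normal distribution". The post-training ratings also undergo "superiority testing, with a margin of 5 points on a 100-point scale". The same section says: "For assessments conducted for each eye separately, the right eye will be used for analysis".

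The document does not mention block size, stratification or joint balance of the two allocations. It also does not say whether training finishes one eye before the other or alternates between eyes.

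**The concern.** Which lens is handled first follows from lens-to-eye and start eye taken together. The stated reason for randomising start eye is handedness and dexterity, not lens order. Each allocation could be well balanced on its own while their combination is not. For people learning a new skill, the second lens might be rated as easier because of practice, or harder because of fatigue.

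If such an effect exists, a chance excess of one order moves the unadjusted lens difference in that particular trial. Order variation also stays in the error term. What is at stake is precision and protection against chance imbalance, using a factor that the trial already randomises. Freedom from systematic bias is not at stake.

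**Working it through.** **Inputs from section 5.2.1.** Two-tailed paired t-test, difference 5 points, effect size 0.60, alpha 0.05, power 0.90, 32 completers, up to 60 randomised. The implied SD of the paired difference is 5/0.60 = 8.33.

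**Plan's own figure.** The noncentrality is 0.60 × √32 = 3.39 on 31 df, which gives power 0.908; n = 31 gives 0.898. The stated 32 is reproduced.

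**Model for order (assumed).** The Precision1-minus-Moist difference is D = τ + d·s + e. Here s is +1 or −1 according to the lens handled first, and d is the size of the shift. The document gives no value for d, so 0 to 5 points is shown. Five points equals the whole difference to be detected, so it is an upper extreme.

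**Chance imbalance among 32 analysed.** The probability of a split of 20:12 or worse is:
- 0.215 under simple randomisation, from Binomial(32, 0.5);
- 0.069 if 60 are blocked and a random 32 are analysed, from Hypergeometric(60, 30, 32). In that case an exact 16:16 split has probability only 0.204.

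At 20:12 the unadjusted estimate moves by d × 8/32 = d/4, that is 0.25, 0.50, 0.75 and 1.25 points for d = 1, 2, 3 and 5.

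**Cost of the term when d = 0.** The standard error of the intercept is 8.33/√(32(1 − x̄²)), where x̄ is the mean of s, on 30 df. Power is 0.907 at exact balance. Averaged over the order split it is 0.903 (60 blocked, 32 analysed) or 0.898 (simple randomisation), against 0.908 for the plain test.

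**Power against zero at a true difference of 5, with 60 blocked and 32 analysed.** Plain-test values are simulated, except the exact 0.908 at d = 0.

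| d | SD excludes order: plain | with term | SD includes order: plain | with term |
|---|---|---|---|---|
| 0 | 0.908 | 0.903 | 0.908 | 0.903 |
| 1 | 0.904 | 0.903 | 0.909 | 0.907 |
| 2 | 0.895 | 0.903 | 0.911 | 0.919 |
| 3 | 0.878 | 0.903 | 0.915 | 0.937 |
| 5 | 0.820 | 0.903 | 0.928 | 0.983 |

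Where 8.33 includes order, the residual SD is √(8.33² − d²).

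**Break-even, SD excluding order.** Under blocking, the plain test falls to 0.903 at about d = 1.25. Under simple randomisation, it falls to the term's 0.898 by about d = 1.75.

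**Type I error of the plain paired test, SD excluding order.** Under simple randomisation it stays at about 0.05. With 60 blocked and 32 analysed it is about 0.042 to 0.043 at d = 3 and 0.035 at d = 5. Blocking keeps order out of the variation of the mean difference but leaves it in the estimated SD, so the test becomes conservative. With the order term it returns to 0.05.

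**The case against.** The strongest reply is that nothing here is defective. Randomising start eye already prevents systematic order bias, and chance imbalance is part of the paired test's error. Silence about blocking does not show that the schedule is unbalanced, and the ANOVA option could carry an order term. A reader might infer that the planned test is biased or has inflated type I error, or that an order effect has been shown. The documents support none of these. Three repetitions per lens and rating only after passing could make any order effect small, as could alternating eyes if that is the practice.

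The limits on the gain also stand:
- At d = 2 the term adds only 0.008 of power (0.903 − 0.895), and below break-even it loses.
- A few more completers would do as much. Under simple randomisation with SD excluding order, 34 give about 0.910 at d = 2 and 36 give about 0.909 at d = 3, within the cap of 60.
- The primary rating precedes dispensing, so up to 60 people might have one. With 60 rated and balanced, the plain test has power of about 0.99 even at d = 5, and little is left to gain.
- The power figures concern the test against zero. If the 5-point margin is a shifted null, a true difference of 5 is rejected only at the alpha level under either model.

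These arguments limit the size of the point. They do not change the fact that lens order is set by two randomised factors whose joint balance is not stated and which the analysis does not name.

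**Conclusion.** The point holds as a cheap, optional improvement and not as an error. The plan as written is valid and unbiased.

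With 32 analysed from 60 blocked and SD 8.33 excluding order, the term gains about 0.8, 2.5 and 8.3 percentage points of power at an assumed 2, 3 and 5 points. It loses about 0.5 points if there is no order effect. The result depends on an order effect for which the document gives no figure, on a random 32 of 60 being analysed, and on the test being against zero. No benefit is claimed for the margin test, for a much larger rated set, or for the order term where the Wilcoxon test is selected.

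The right-eye rule is a separate and larger problem. A paired lens comparison needs both eyes, and under a right-eye-only analysis there is no within-participant difference to adjust.

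**What to change.** - **Schedule.** Generate one schedule blocked over the four combinations (Precision1 on right or left eye × start eye right or left), and state whether training alternates eyes.
- **Analysis.** Where the normality rule in section 11.1 selects a parametric test, model the within-participant Precision1-minus-Moist difference, separately for insertion and removal, with one +1/-1 term for the lens handled first. The intercept is the lens effect. Where the rule selects Wilcoxon, keep it; only the blocking then applies.
- **Keep the two together.** Blocking without the term makes the plain paired test conservative if an order effect exists. If that test is reported as a sensitivity analysis, say so there.
- **Separately.** Reconcile the right-eye rule with the two-eye lens comparison.

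The cost is schedule set-up, one model term per rating, one degree of freedom, and the small loss of power shown above when the order effect is below break-even. An additional eye term is not proposed: it would lower 0.903 to about 0.897, and no benefit from it has been quantified.

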5.2 STUDY POPULATION

5.2.1 SAMPLE SIZE CALCULATION

The sample size required for a 2-tailed matched paired t-test to detect a change of 5 points in subjective ratings of handling for insertion and removal, with α =0.05, power = 0.90, and an effect size of 0.60 is 32 to complete the study and be eligible for data analysis (a sample size of 32 participants excluding possible dropouts and screen failures).

Up to 60 participants may be randomized to and dispensed with 1-Day ACUVUE Moist and Precision1 DD CLs, to account for potential drop-out in neophytes e.g. due to adaptation/handling issues.

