5.2.2 NUMBER OF PARTICIPANTS

Up to 60 participants may be recruited using CORE records and advertising approved by the UW Office of Research Ethics. Up to 60 participants may be randomized to and dispensed with study products, with a target of number of 32 participants completing the study. Informed consent will be obtained for all participants prior to their enrolment in the study (Appendix 1).

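### Start-eye randomisation balances only practice order; the eye-side (handedness) effect is balanced by the lens-to-eye randomisation, and section 11.1 should carry that factor as a term to gain precision

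*Combined protocol and SAP*

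**What the plan says.** Section 5.1.2 randomises two things. The first is lens to eye: "The schedule will determine which lens type (L1 or L2) will be worn on which eye for each participant". The second is order: the "start eye for insertion/removal training will also be randomized to prevent any potential bias due to handedness/dexterity". Section 5.4.2 (Visit 1, Part B) repeats the handedness purpose, again attached to the start eye. Under 5.4.2 each eye keeps its lens type through training, retraining and the week of wear. No blocking of the lens-to-eye allocation is stated.

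The primary outcome is ease of insertion and ease of removal, rated 0-100 for each eye after successful training. Sections 5.4.2 and 5.5.1 list age and sex as demographics; the dominant hand is not listed.

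Section 11.1 plans the comparison as follows: "Differences between lenses and differences over time will be compared using either Paired t-tests or Wilcoxon matched pairs, or using ANOVA, as applicable". It names no term for eye, lens-to-eye group or order, and it moves to non-parametric tests when data are not normal. It also says that the right eye is analysed for assessments made on each eye separately.

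**The concern.** A neophyte may find one eye easier to handle whatever the lens, for example because of the dominant hand. Changing which eye starts does not alter that, because the easier eye remains tied to the same lens. The protocol thus names a threat to its primary outcome and credits the wrong step with controlling it.

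Because wear is contralateral, the eye-side effect is part of every paired difference. Lens-to-eye randomisation gives it a random sign, so it averages to zero, but it still widens the spread of the differences. If more analysed participants have Precision1 on the easier eye than on the harder one, part of the eye effect also appears in the lens estimate. At stake are the precision of the insertion and removal comparisons and the credibility of a small lens difference in a sample of 32.

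**Working it through.** **Inputs from the documents (5.2.1, 5.2.2).** "The sample size required for a 2-tailed matched paired t-test to detect a change of 5 points in subjective ratings of handling"; two-sided alpha 0.05; "power = 0.90, and an effect size of 0.60 is 32 to complete the study". The implied SD of the paired difference is 5/0.60 = 8.33. Up to 60 may be randomised to obtain 32 completers.

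**Assumption.** Let e be the easier-eye minus harder-eye rating difference in points. The documents give no figure, so 3 and 5 points are used for illustration.

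**1. The plan's own figure.** Paired t-test, noncentral t, d = 0.60: power is 0.898 at n = 31 and 0.908 at n = 32. The stated 32 reproduces.

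**2. Model.** Difference = lens effect + e (Precision1 on the easier eye) or lens effect - e (on the harder eye), plus residual. With a random sign, the eye part has mean 0 and variance e².

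**3. Validity of the unadjusted test.** In 100,000 simulated trials of 32 per setting, with simple randomisation and no lens effect, the mean estimate was within about 0.01 point of zero. Type I error was 0.048 to 0.051 for e from 0 to 8.

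**4. Power if 8.33 is the total paired SD, e included, and all share the same easier eye.** Residual SD with the term = √(8.33² - e²), 30 df, 16:16 split.
- e = 3: residual SD 7.77, power 0.941, against 0.908 without the term.
- e = 5: residual SD 6.67, power 0.984, against 0.908.

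**5. Power if 8.33 excludes e, all sharing the same easier eye.** Unadjusted SD = √(8.33² + e²).
- e = 3: SD 8.86, power 0.871.
- e = 5: SD 9.72, power 0.805.
- With the term: residual SD 8.33, 30 df, power 0.907 at 16:16.

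Those unadjusted figures treat the sign as random, while 0.907 is for an even split. Simulated like for like, unadjusted versus adjusted:

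| Split | e = 3 | e = 5 |
|---|---|---|
| Simple randomisation | 0.872 vs 0.899 | 0.805 vs 0.897 |
| 16:16 | 0.885 vs 0.908 | 0.837 vs 0.907 |

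**6. If participants differ in their easier eye.** A right/left term removes only the average side effect. Take e = 5, 8.33 excluding e, and 80% sharing the easier eye. The average effect is (0.8 - 0.2) × 5 = 3 points. The variance left in the residual is 25 × (1 - 0.6²) = 16, so the residual SD is √(69.44 + 16) = 9.24 and adjusted power is 0.841. At a 50:50 mix the residual SD is 9.72 and adjusted power 0.804, so nothing is gained over 0.805.

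**7. Uneven split.** Shift of the unadjusted mean = e(n1 - n2)/32. At 20:12 this is 8e/32 = e/4: 0.75 points at e = 3 and 1.25 at e = 5, all sharing the same easier eye. If 80% share it, the shift at e = 5 is 3/4 = 0.75 points. Under simple randomisation, 20:12 or worse in either direction has probability 0.215. Given a 20:12 split, the simulated unadjusted type I error is 0.063 (e = 3) and 0.074 (e = 5). At 16:16 the unadjusted test is conservative: 0.039 and 0.023.

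**8. Cost of the term if there is no eye effect.** At 16:16, power goes from 0.908 to 0.907, a loss of 0.001. At 20:12 the standard error uses √((1/20 + 1/12)/4) = 0.183 in place of 1/√32 = 0.177. Power is then 0.889, a loss of 0.019.

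**The case against.** The strongest reply is that the design already handles the problem. Lens type is randomised to eye in the same section, the eye effect has mean zero, and the unadjusted paired test keeps its 5% error rate. That stands in full. A reader might infer from the misattributed purpose that handedness is uncontrolled and biases the lens comparison; the lens-to-eye randomisation rules that out.

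The second reply is that no power need be lost. The effect size of 0.60 was stated for a matched paired t-test, so 8.33 is most naturally the total SD with any eye effect in it. That also stands: on this reading the stated power of 0.908 holds and the term is a gain. A reader might conclude from step 5 that the trial is underpowered, but this needs 8.33 to exclude the eye effect, which the documents do not say.

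Third, section 11.1 leaves ANOVA open, so an eye term is not excluded. True, but none is specified, and choosing a model after unmasking is what pre-specification is meant to avoid.

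Two further inferences fail. The eye effect is in the differences because wear is contralateral, not because the dominant hand goes unrecorded; the randomisation schedule alone is enough to fit the term. And an uncontrolled start eye at home does not explain the issue at Visit 2, since start eye governs only order. The Visit 2 per-eye ratings carry the eye effect because each eye keeps its lens.

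**Conclusion.** The point holds as a precision improvement and a correction of wording. Sections 5.1.2 and 5.4.2 credit start-eye randomisation with a protection that comes from lens-to-eye randomisation, and section 11.1 does not specify the randomised factor that would take the eye effect out of the differences.

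The size depends on e, which is assumed. For e of 3 to 5 points and a shared easier eye, the gain at n = 32 is 0.03 to 0.08 of power if 8.33 is the total SD (0.908 to 0.941 or 0.984). If 8.33 excludes e, the contrast is 0.871 or 0.805 against 0.907. The gain falls as participants differ in their easier eye and is nil at an even mix. Chance imbalance matters only conditionally: at 20:12 and e = 5, the 1.25-point shift is a quarter of the 5-point superiority margin in 11.1.

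**What to change.** **Section 11.1.** Analyse each participant's Precision1-minus-Moist difference, for the primary ratings and the Visit 2 per-eye ratings, in a linear model with the randomised lens-to-eye group coded +1/2 and -1/2; the intercept is the lens effect. For non-normal data, name a rank test that takes account of the lens-to-eye strata. One workable form is a rank-sum comparison of right-minus-left differences between the two groups, in which an average eye-side effect cancels. State that the right-eye rule does not apply to these ratings; applied to them, it would remove the pairing on which this model and the sample size rest.

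**Section 5.1.2 (and the matching line in 5.4.2).** State that lens-to-eye allocation is blocked and is what balances the eye-side or handedness effect, and that start-eye randomisation balances practice order. Blocking those randomised does not guarantee balance among those who pass training and are analysed, so the model term is still needed.

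**Optional.** Record the dominant hand and repeat the analysis with the factor coded as Precision1 on the dominant-hand side. This can recover what a right/left term misses if the easier eye follows the hand.

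**Cost.** A few sentences, one degree of freedom and, if taken up, one demographics question. If there is no eye effect, the term costs about 0.001 of power at 16:16 and 0.019 at 20:12. No visit or participant is added.
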